#### [name]

- d. Metformin 1700 mg + glibenclamide 10 mg  $\rightarrow$  metformin 850 mg + glibenclamide 2.5 mg
- e. Metformin 2550 mg + glibenclamide 2.5-5 mg  $\rightarrow$  metformin 1700 mg
- f. Metformin 2550 mg + glibenclamide 10 mg → metformin 1700 mg + glibenclamide 2.5 mg
   16. Metformin and glibenclamide, problems with metformin, nonadherent
  - a. Metformin 850 mg + glibenclamide any dose, agrees to take metformin  $\rightarrow$  metformin 850 mg
    - b. Metformin 850 mg + glibenclamide any dose, refuses to take metformin → stop medications, recheck A1c in 3 months
    - c. Metformin 1700 mg + glibenclamide any dose  $\rightarrow$  metformin 850 mg
    - d. Metformin 2550 mg + glibenclamide any dose → metformin 1700 mg
- 17. Metformin and glibenclamide, hypoglycemia or hypoglycemia symptoms, adherent
  - a. Metformin 850 mg + glibenclamide 2.5-5 mg → metformin 850 mg
  - b. Metformin 850 mg + glibenclamide 10 mg  $\rightarrow$  metformin 1700 mg
  - c. Metformin 1700-2550 mg + glibenclamide any dose  $\rightarrow$  metformin 1700 mg
- 18. Metformin and glibenclamide, hypoglycemia or hypoglycemia symptoms, nonadherent  $\rightarrow$  same as #14
- 19. Metformin and glibenclamide, problems with metformin, hypoglycemia or hypoglycemia symptoms, adherent
  - a. Metformin 850 mg + glibenclamide any dose, agrees to take metformin → metformin 850 mg
    - b. Metformin 850 mg + glibenclamide any dose, refuses to take metformin  $\rightarrow$  stop medications, recheck A1c in 3 months
    - c. Metformin 1700 mg + glibenclamide any dose  $\rightarrow$  metformin 850 mg
  - d. Metformin 2550 mg + glibenclamide any dose  $\rightarrow$  metformin 1700 mg
- 20. Metformin and glibenclamide, problems with metformin, hypoglycemia or hypoglycemia symptoms, nonadherent  $\rightarrow$  same as #16

#### 6≤ A1c ≤Tx goal

- 1. Metformin without problems, adherent
  - a. Metformin 850 mg  $\rightarrow$  metformin 850 mg
  - b. Metformin 1700 mg  $\rightarrow$  metformin 1700 mg
  - c. Metformin 2550 mg  $\rightarrow$  metformin 2550 mg
- 2. Metformin without problems, nonadherent
  - a. Metformin 850 mg  $\rightarrow$  metformin 850 mg
  - b. Metformin 1700-2550 mg  $\rightarrow$  metformin 1700 mg
- 3. Metformin with problems, adherent
  - a. Metformin 850 mg, agrees to take metformin  $\rightarrow$  metformin 850 mg
  - b. Metformin 850 mg, refuses to take metformin  $\rightarrow$  glibenclamide 2.5 mg
  - c. Metformin 1700 mg  $\rightarrow$  metformin 850 mg
  - d. Metformin 2550 mg  $\rightarrow$  metformin 1700 mg
- 4. Metformin with problems, nonadherent  $\rightarrow$  same as #3
- Glibenclamide without problems, no previous problems with metformin, adherent

   All doses → metformin 1700 mg
- 6. Glibenclamide without problems, no previous problems with metformin, nonadherent  $\rightarrow$  same as #5
- 7. Glibenclamide without problems, previous problems with metformin, adherent
  - a. Willing to take metformin
    - i. Glibenclamide 2.5 mg  $\rightarrow$  metformin 850 mg
    - ii. Glibenclamide 5 mg  $\rightarrow$  metformin 850 mg + glibenclamide 2.5 mg
  - iii. Glibenclamide 10 mg  $\rightarrow$  metformin 850 mg + glibenclamide 5 mg
  - b. Refuses to take metformin  $\rightarrow$  current dose of glibenclamide

Version #: 1.0

#### [name]

- $\hbox{8. Glibenclamide without problems, previous problems with metformin, nonadherent } \\$ 
  - a. Willing to take metformin
    - i. Glibenclamide 2.5 mg  $\rightarrow$  metformin 850 mg
    - ii. Glibenclamide 5 mg  $\rightarrow$  metformin 850 mg + glibenclamide 2.5 mg
    - iii. Glibenclamide 10 mg  $\rightarrow$  metformin 850 mg + glibenclamide 5 mg
  - b. Refuses to take metformin
    - i. Glibenclamide 2.5 mg  $\rightarrow$  stop medications, recheck A1c in last 3 months
    - ii. Glibenclamide 5 mg  $\rightarrow$  glibenclamide 2.5 mg
    - iii. Glibenclamide 10 mg  $\rightarrow$  glibenclamide 5 mg
- 9. Glibenclamide with hypoglycemia or hypoglycemia symptoms, no previous problems with metformin, adherent  $\rightarrow$  same as #5
- 10. Glibenclamide with hypoglycemia or hypoglycemia symptoms, no previous problems with metformin, nonadherent  $\rightarrow$  same as #5
- 11. Glibenclamide with hypoglycemia or hypoglycemia symptoms, previous problems with metformin, adherent
  - a. Agrees to take metformin
    - i. Glibenclamide 2.5-5 mg  $\rightarrow$  metformin 850 mg
    - ii. Glibenclamide 10 mg  $\rightarrow$  metformin 850 mg + glibenclamide 2.5 mg
  - b. Refuses to take metformin
    - i. Glibenclamide 2.5 mg  $\rightarrow$  stop medications, recheck A1c in 3 months
    - ii. Glibenclamide 5 mg  $\rightarrow$  glibenclamide 2.5 mg
    - iii. Glibenclamide 10 mg  $\rightarrow$  glibenclamide 5 mg
- 12. Glibenclamide with hypoglycemia or hypoglycemia symptoms, previous problems with metformin, nonadherent → same as #11
- 13. Metformin and glibenclamide without problems, adherent  $\rightarrow$  continue current doses
- 14. Metformin and glibenclamide without problems, nonadherent
  - a. Metformin any dose + glibenclamide 2.5 mg  $\rightarrow$  metformin current dose
  - b. Metformin any dose + glibenclamide 5 mg  $\rightarrow$  metformin current dose + glibenclamide 2.5 mg
  - c. Metformin any dose + glibenclamide 10 mg  $\rightarrow$  metformin current dose + glibenclamide 5 mg
- 15. Metformin and glibenclamide, problems with metformin, adherent
  - a. Metformin 850 mg + glibenclamide any dose, agrees to take metformin →metformin 850 mg + current glibenclamide dose
  - b. Metformin 850 mg + glibenclamide any dose, refuses to take metformin → current glibenclamide dose
  - c. Metformin 1700 mg + glibenclamide any dose  $\rightarrow$  metformin 850 mg + current glibenclamide dose
  - d. Metformin 2550 mg + glibenclamide any dose  $\rightarrow$  metformin 1700 mg + current glibenclamide dose
- 16. Metformin and glibenclamide, problems with metformin, nonadherent
  - a. Agrees to take metformin
    - i. Metformin 850 mg + glibenclamide 2.5 mg  $\rightarrow$  metformin 850 mg
    - ii. Metformin 850 mg + glibenclamide 5 mg  $\rightarrow$  metformin 850 mg + glibenclamide 2.5 mg
    - iii. Metformin 850 mg + glibenclamide 10 mg  $\rightarrow$  metformin 850 mg+ glibenclamide 5 mg
  - b. Refuses to take metformin
    - i. Metformin 850 mg + glibenclamide 2.5 mg  $\rightarrow$  stop medications, recheck A1c in 3 months
    - ii. Metformin 850 mg + glibenclamide 5 mg  $\rightarrow$  glibenclamide 2.5 mg
    - iii. Metformin 850 mg + glibenclamide 10 mg  $\rightarrow$  glibenclamide 5 mg
  - c. Metformin 1700 mg + glibenclamide 2.5 mg  $\rightarrow$  metformin 850 mg

Version #: 1.0

[name]

- d. Metformin 1700 mg + glibenclamide 5 mg  $\rightarrow$  metformin 850 mg + glibenclamide 2.5 mg
- e. Metformin 1700 mg + glibenclamide 10 mg  $\rightarrow$  metformin 850 mg + glibenclamide 5 mg
- f. Metformin 2550 mg + glibenclamide 2.5 mg → metformin 1700 mg
- g. Metformin 2550 mg + glibenclamide 5 mg  $\rightarrow$  metformin 1700 mg + glibenclamide 2.5 mg
- h. Metformin 2550 mg + glibenclamide 10 mg  $\rightarrow$  metformin 1700 mg + glibenclamide 5 mg
- 17. Metformin and glibenclamide, hypoglycemia or hypoglycemia symptoms, adherent
  - a. Metformin any dose + glibenclamide 2.5 mg  $\rightarrow$  metformin current dose
  - b. Metformin any dose + glibenclamide 5 mg → metformin current dose + glibenclamide 2.5 mg
  - c. Metformin any dose + glibenclamide 10 mg  $\rightarrow$  metformin current dose + glibenclamide 5 mg
- 18. Metformin and glibenclamide, hypoglycemia or hypoglycemia symptoms, nonadherent → same as #17
- 19. Metformin and glibenclamide, problems with metformin, hypoglycemia or hypoglycemia symptoms, adherent
  - a. Agrees to take metformin
    - i. Metformin 850 mg + glibenclamide 2.5 mg  $\rightarrow$  metformin 850 mg
    - ii. Metformin 850 mg + glibenclamide 5 mg  $\rightarrow$  metformin 850 mg + glibenclamide 2.5 mg
    - iii. Metformin 850 mg + glibenclamide 10 mg  $\rightarrow$  metformin 850 mg+ glibenclamide 5 mg
  - b. Refuses to take metformin
    - i. Metformin 850 mg + glibenclamide 2.5 mg  $\rightarrow$  stop medications, recheck A1c in 3 months
    - ii. Metformin 850 mg + glibenclamide 5 mg  $\rightarrow$  glibenclamide 2.5 mg
    - iii. Metformin 850 mg + glibenclamide 10 mg  $\rightarrow$  glibenclamide 5 mg
  - c. Metformin 1700 mg + glibenclamide 2.5 mg  $\rightarrow$  metformin 850 mg
  - d. Metformin 1700 mg + glibenclamide 5 mg  $\rightarrow$  metformin 850 mg + glibenclamide 2.5 mg
  - e. Metformin 1700 mg + glibenclamide 10 mg  $\rightarrow$  metformin 850 mg + glibenclamide 5 mg
  - f. Metformin 2550 mg + glibenclamide 2.5 mg  $\rightarrow$  metformin 1700 mg
  - g. Metformin 2550 mg + glibenclamide 5 mg → metformin 1700 mg + glibenclamide 2.5 mg
  - h. Metformin 2550 mg + glibenclamide 10 mg  $\rightarrow$  metformin 1700 mg + glibenclamide 5 mg
- 20. Metformin and glibenclamide, problems with metformin, hypoglycemia or hypoglycemia symptoms, nonadherent → same as #19

# Tx goal< A1c <9 AND FBG >130(150) OR PPBG >180(200

- 1. Metformin without problems, adherent
  - a. Metformin 850 mg  $\rightarrow$  metformin 1700 mg
  - b. Metformin 1700 mg  $\rightarrow$  metformin 2550 mg
  - c. Metformin 2550 mg  $\rightarrow$  metformin 2550 mg + glibenclamide 2.5 mg
- 2. Metformin without problems, nonadherent
  - a. Metformin 850 mg  $\rightarrow$  metformin 1700 mg
  - b. Metformin 1700 mg  $\rightarrow$  metformin 1700 mg
  - c. Metformin 2550 mg  $\rightarrow$  metformin 2550 mg
- 3. Metformin with problems, adherent
  - a. Metformin 850 mg, agrees to take metformin  $\rightarrow$  metformin 850 mg + glibenclamide 2.5 mg
  - b. Metformin 850 mg, refuses to take metformin  $\rightarrow$  glibenclamide 2.5 mg
  - c. Metformin 1700 mg  $\rightarrow$  metformin 850 mg + glibenclamide 2.5 mg
  - d. Metformin 2550 mg  $\rightarrow$  metformin 1700 mg + glibenclamide 2.5 mg
- 4. Metformin with problems, nonadherent  $\rightarrow$  same as #3
- 5. Glibenclamide without problems, no previous problems with metformin, adherent
  - a. Any dose  $\rightarrow$  metformin 1700 mg + glibenclamide current dose
- 6. Glibenclamide without problems, no previous problems with metformin, nonadherent

Version #: 1.0

[name]

- a. All doses  $\rightarrow$  metformin 1700 mg
- 7. Glibenclamide without problems, previous problems with metformin, adherent
  - Glibenclamide any dose, agrees to take metformin → metformin 850 mg + current glibenclamide dose
  - b. Refuses to take metformin
    - i. Glibenclamide 2.5 mg  $\rightarrow$  glibenclamide 5 mg
    - ii. Glibenclamide 5 mg  $\rightarrow$  glibenclamide 10 mg
    - iii. Glibenclamide 10 mg  $\rightarrow$  glibenclamide 10 mg
- 8. Glibenclamide without problems, previous problems with metformin, nonadherent
  - a. Willing to take metformin
    - i. Glibenclamide 2.5 mg  $\rightarrow$  metformin 850 mg
    - ii. Glibenclamide 5 mg  $\rightarrow$  metformin 850 mg + glibenclamide 2.5 mg
    - iii. Glibenclamide 10 mg  $\rightarrow$  metformin 850 mg + glibenclamide 5 mg
    - b. Refuses to take metformin  $\rightarrow$  continue current glibenclamide dose
- 9. Glibenclamide with hypoglycemia or hypoglycemia symptoms, no previous problems with metformin, adherent
  - a. Glibenclamide 2.5-5 mg  $\rightarrow$  metformin 1700 mg
  - b. Glibenclamide 10 mg  $\rightarrow$  metformin 1700 mg + glibenclamide 2.5 mg
- 10. Glibenclamide with hypoglycemia or hypoglycemia symptoms, no previous problems with metformin, nonadherent → same as #9
- 11. Glibenclamide with hypoglycemia or hypoglycemia symptoms, previous problems with metformin, adherent
  - a. Agrees to take metformin
    - i. Glibenclamide 2.5 mg  $\rightarrow$  metformin 850 mg
    - ii. Glibenclamide 5 mg  $\rightarrow$  metformin 850 mg + glibenclamide 2.5 mg
    - iii. Glibenclamide 10 mg  $\rightarrow$  metformin 850 mg + glibenclamide 5 mg
  - b. Refuses to take metformin
    - i. Glibenclamide 2.5 mg  $\rightarrow$  MD consult
    - ii. Glibenclamide 5 mg  $\rightarrow$  glibenclamide 2.5 mg
    - iii. Glibenclamide 10 mg  $\rightarrow$  glibenclamide 5 mg
- 12. Glibenclamide with hypoglycemia or hypoglycemia symptoms, previous problems with metformin, nonadherent  $\rightarrow$  same as #11
- 13. Metformin and glibenclamide without problems, adherent
  - a. Metformin 850 mg + glibenclamide any dose → metformin 1700 mg + current glibenclamide dose
     b. Metformin 1700 mg + glibenclamide any dose → metformin 2550 mg + glibenclamide current dose
  - c. Metformin 2550 mg + glibenclamide 2.5 mg → metformin 2550 mg + glibenclamide 5 mg
  - d. Metformin 2550 mg + glibenclamide 5 mg  $\rightarrow$  metformin 2550 mg + glibenclamide 10 mg
  - e. Metformin 2550 mg + glibenclamide 10 mg → metformin 2550 mg + glibenclamide 10 mg
- 14. Metformin and glibenclamide without problems, nonadherent  $\rightarrow$  continue current doses
- 15. Metformin and glibenclamide, problems with metformin, adherent
  - a. Agrees to take metformin
    - i. Metformin 850 mg + glibenclamide 2.5 mg  $\rightarrow$  metformin 850 mg + glibenclamide 5 mg
    - ii. Metformin 850 mg + glibenclamide 5 mg  $\rightarrow$  metformin 850 mg + glibenclamide 10 mg
    - iii. Metformin 850 mg + glibenclamide 10 mg  $\rightarrow$  metformin 850 mg + glibenclamide 10 mg
    - b. Refuses to take metformin
      - i. Metformin 850 mg + glibenclamide 2.5 mg  $\rightarrow$  glibenclamide 5 mg

[name]

- ii. Metformin 850 mg + glibenclamide 5 mg  $\rightarrow$  glibenclamide 10 mg
- iii. Metformin 850 mg + glibenclamide 10 mg → glibenclamide 10 mg
- c. Metformin 1700 mg + glibenclamide 2.5 mg  $\rightarrow$  metformin 850 mg + glibenclamide 5 mg
- d. Metformin 1700 mg + glibenclamide 5 mg  $\rightarrow$  metformin 850 mg + glibenclamide 10 mg
- e. Metformin 1700 mg + glibenclamide 10 mg  $\rightarrow$  metformin 850 mg + glibenclamide 10 mg
- f. Metformin 2550 mg + glibenclamide 2.5 mg  $\rightarrow$  metformin 1700 mg + glibenclamide 5 mg
- g. Metformin 2550 mg + glibenclamide 5 mg  $\rightarrow$  metformin 1700 mg + glibenclamide 10 mg
- h. Metformin 2550 mg + glibenclamide 10 mg  $\rightarrow$  metformin 1700 mg + glibenclamide 10 mg

16. Metformin and glibenclamide, problems with metformin, nonadherent

- a. Metformin 850 mg + glibenclamide any dose, agrees to take metformin → metformin 850 mg + current glibenclamide dose
  - Metformin 850 mg + glibenclamide any dose, refuses to take metformin → current glibenclamide dose
  - c. Metformin 1700 mg + glibenclamide any dose  $\rightarrow$  metformin 850 mg + current glibenclamide dose
- d. Metformin 2550 mg + glibenclamide any dose → metformin 1700 mg + current glibenclamide dose

17. Metformin and glibenclamide, hypoglycemia or hypoglycemia symptoms, adherent

- a. Metformin 850 mg + glibenclamide 2.5 mg  $\rightarrow$  metformin 1700 mg
- b. Metformin 850 mg + glibenclamide 5 mg → metformin 1700 mg + glibenclamide 2.5 mg
- c. Metformin 850 mg + glibenclamide 10 mg  $\rightarrow$  metformin 1700 mg + glibenclamide 5 mg
- d. Metformin 1700 mg + glibenclamide 2.5 mg  $\rightarrow$  metformin 2550 mg
- e. Metformin 1700 mg + glibenclamide 5 mg  $\rightarrow$  metformin 2550 mg + glibenclamide 2.5 mg
- f. Metformin 1700 mg + glibenclamide 10 mg  $\rightarrow$  metformin 2550 mg + glibenclamide 5 mg
- g. Metformin 2550 mg + glibenclamide 2.5 mg  $\rightarrow$  metformin 2550 mg
- h. Metformin 2550 mg + glibenclamide 5 mg → metformin 2550 mg + glibenclamide 2.5 mg
- i. Metformin 2550 mg + glibenclamide 10 mg  $\rightarrow$  metformin 2550 mg + glibenclamide 5 mg

Metformin and glibenclamide, hypoglycemia or hypoglycemia symptoms, nonadherent → same as #17
 Metformin and glibenclamide, problems with metformin, hypoglycemia or hypoglycemia symptoms,

- adherent
  - a. Agrees to take metformin
    - i. Metformin 850 mg + glibenclamide 2.5 mg → metformin 850 mg
    - ii. Metformin 850 mg + glibenclamide 5 mg  $\rightarrow$  metformin 850 mg + glibenclamide 2.5 mg
    - iii. Metformin 850 mg + glibenclamide 10 mg  $\rightarrow$  metformin 850 mg + glibenclamide 5 mg
  - b. Refuses to take metformin
    - i. Metformin 850 mg + glibenclamide 2.5 mg  $\rightarrow$  MD consult
    - ii. Metformin 850 mg + glibenclamide 5 mg  $\rightarrow$  glibenclamide 2.5 mg
    - iii. Metformin 850 mg + glibenclamide 10 mg  $\rightarrow$  glibenclamide 5 mg
  - c. Metformin 1700 mg + glibenclamide 2.5 mg  $\rightarrow$  metformin 850 mg
  - d. Metformin 1700 mg + glibenclamide 5 mg  $\rightarrow$  metformin 850 mg + glibenclamide 2.5 mg
  - e. Metformin 1700 mg + glibenclamide 10 mg  $\rightarrow$  metformin 850 mg + glibenclamide 5 mg
  - f. Metformin 2550 mg + glibenclamide 2.5 mg → metformin 1700 mg
  - g. Metformin 2550 mg + glibenclamide 5 mg  $\rightarrow$  metformin 1700 mg + glibenclamide 2.5 mg
  - h. Metformin 2550 mg + glibenclamide 10 mg → metformin 1700 mg + glibenclamide 5 mg

20. Metformin and glibenclamide, problems with metformin, hypoglycemia or hypoglycemia symptoms, nonadherent → same as #19

Version #: 1.0

[name]

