#### Tx goal< A1c <9

- Not taking medications or nonadherent, no hypoglycemia or hypoglycemia symptoms, no problems with metformin → metformin 1700 mg
- 2. Not taking medications or nonadherent, no hypoglycemia or hypoglycemia symptoms, problems with metformin
  - a. Agrees to take metformin  $\rightarrow$  metformin 850 mg + glibenclamide 2.5 mg
  - b. Refuses to take metformin  $\rightarrow$  glibenclamide 2.5 mg
- 3. Not taking medications or nonadherent, hypoglycemia or hypoglycemia symptoms → metformin 1700 mg
- 4. Not taking medications or nonadherent, hypoglycemia or hypoglycemia symptoms, problems with metformin
  - a. Agrees to take metformin  $\rightarrow$  metformin 850 mg
  - b. Refuses to take metformin, prescribed glibenclamide >2.5 mg  $\rightarrow$  glibenclamide 2.5 mg
  - c. Refuses to take metformin, prescribed glibenclamide 2.5 mg  $\rightarrow$  MD consult
- 5. Taking metformin without problems
  - a. Metformin 500-1000 mg  $\rightarrow$  metformin 1700 mg
  - b. Metformin 1500-2000 mg → metformin 2550 mg
  - c. Metformin 2550 mg  $\rightarrow$  metformin 2550 mg + glibenclamide 2.5 mg
- 6. Taking metformin with problems
  - a. Metformin 500-850 mg, agrees to take metformin → metformin 850 mg + glibenclamide 2.5 mg

[name]

- b. Metformin 500-850 mg, refuses to take metformin  $\rightarrow$  glibenclamide 2.5 mg
- c. Metformin 1000-1700 mg  $\rightarrow$  metformin 850 mg + glibenclamide 2.5 mg
- d. Metformin 2000-2550 mg  $\rightarrow$  metformin 1700 mg + glibenclamide 2.5 mg
- 7. Taking glibenclamide without problems
  - a. Glibenclamide 2.5-10 mg  $\rightarrow$  metformin 1700 mg + glibenclamide current dose
  - b. Glibenclamide 15-20 mg → metformin 1700 mg + glibenclamide 10 mg
- 8. Taking glibenclamide, previous problems with metformin
- a. Agrees to take metformin
  - i. Glibenclamide 2.5-10 mg  $\rightarrow$  metformin 850 mg + glibenclamide current dose
  - ii. Glibenclamide 15-20 mg  $\rightarrow$  metformin 850 mg + glibenclamide 10 mg
  - b. Refuses to take metformin
    - i. Glibenclamide 2.5 mg  $\rightarrow$  glibenclamide 5 mg
    - ii. Glibenclamide 5 mg  $\rightarrow$  glibenclamide 10 mg
- iii. Glibenclamide 10-20 mg  $\rightarrow$  glibenclamide 10 mg
- 9. Taking glibenclamide with hypoglycemia or hypoglycemia symptoms
  - a. Glibenclamide 2.5 mg  $\rightarrow$  metformin 1700 mg
  - b. Glibenclamide 5 mg  $\rightarrow$  metformin 1700 mg + glibenclamide 2.5 mg

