#### 180(200)≤FBG<400 or 300≤PPBG<HI

- 1. Metformin without problems, adherent
  - a. Metformin 850 mg  $\rightarrow$  metformin 1700 mg
  - b. Metformin 1700 mg  $\rightarrow$  metformin 2550 mg
  - c. Metformin 2550 mg → metformin 2550 mg + glibenclamide 2.5 mg
- 2. Metformin without problems, nonadherent  $\rightarrow$  continue current doses
- 3. Metformin with problems, adherent
  - a. Metformin 850 mg, willing to continue → metformin 850 mg + glibenclamide 2.5 mg
  - b. Metformin 850 mg, not willing to continue  $\rightarrow$  glibenclamide 2.5 mg
  - c. Metformin 1700 mg  $\rightarrow$  metformin 850 mg + glibenclamide 2.5 mg
  - d. Metformin 2550 mg  $\rightarrow$  metformin 1700 mg + glibenclamide 2.5 mg
- 4. Metformin with problems, nonadherent  $\rightarrow$  same as #3
- 5. Glibenclamide without problems, no previous problems with metformin, took yesterday
  - a. Glibenclamide 2.5 mg  $\rightarrow$  metformin 1700 mg + glibenclamide 2.5 mg
  - b. Glibenclamide 5 mg  $\rightarrow$  metformin 1700 mg + glibenclamide 5 mg
  - c. Glibenclamide 10 mg  $\rightarrow$  metformin 1700 mg + glibenclamide 10 mg
- 6. Glibenclamide without problems, no previous problems with metformin, did not take yesterday
  - a. Glibenclamide 2.5 mg  $\rightarrow$  metformin 1700 mg
  - b. Glibenclamide 5 mg  $\rightarrow$  metformin 1700 mg + glibenclamide 2.5 mg
  - c. Glibenclamide 10 mg  $\rightarrow$  metformin 1700 mg + glibenclamide 5 mg
[name]

- 7. Glibenclamide without problems, previous problems with metformin, took yesterday
  - a. Agrees to take metformin  $\rightarrow$  metformin 850 mg + current glibenclamide dose
  - b. Refuses to take metformin
    - i. Glibenclamide 2.5 mg  $\rightarrow$  glibenclamide 5 mg
    - ii. Glibenclamide 5 mg  $\rightarrow$  glibenclamide 10 mg
    - iii. Glibenclamide 10 mg  $\rightarrow$  glibenclamide 10 mg
- 8. Glibenclamide without problems, previous problems with metformin, did not take yesterday  $\rightarrow$  same as #7
- 9. Glibenclamide with hypoglycemia symptoms, no previous problems with metformin, took yesterday
  - a. Glibenclamide 2.5 mg  $\rightarrow$  metformin 1700 mg
  - b. Glibenclamide 5 mg  $\rightarrow$  metformin 1700 mg + glibenclamide 2.5 mg
  - c. Glibenclamide 10 mg  $\rightarrow$  metformin 1700 mg + glibenclamide 5 mg
- 10. Glibenclamide with hypoglycemia or hypoglycemia symptoms, no previous problems with metformin, did not take yesterday → same as #9

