# Tx goal< A1c <9 AND [FBG ≤130(150) OR PPBG ≤180(200)] → Use dosing recommendations for 6≤ A1c ≤Tx goal

# 9≤ A1c ≤14 AND FBG >130(150) OR PPBG >180(200)

- 1. Metformin without problems, adherent
  - a. Metformin 850 mg  $\rightarrow$  metformin 1700 mg + glibenclamide 2.5 mg
  - b. Metformin 1700 mg  $\rightarrow$  metformin 1700 mg + glibenclamide 2.5 mg
  - c. Metformin 2550 mg  $\rightarrow$  metformin 2550 mg + glibenclamide 2.5 mg
- 2. Metformin without problems, nonadherent
  - a. Metformin 850 mg  $\rightarrow$  metformin 1700 mg
  - b. Metformin 1700 mg  $\rightarrow$  metformin 1700 mg
  - c. Metformin 2550 mg  $\rightarrow$  metformin 2550 mg
- 3. Metformin with problems, adherent
  - a. Metformin 850 mg, agrees to take metformin  $\rightarrow$  metformin 850 mg + glibenclamide 2.5 mg
  - b. Metformin 850 mg, refuses to take metformin  $\rightarrow$  glibenclamide 2.5 mg
  - c. Metformin 1700 mg  $\rightarrow$  metformin 850 mg + glibenclamide 2.5 mg
  - d. Metformin 2550 mg → metformin 1700 mg + glibenclamide 2.5 mg
- 4. Metformin with problems, nonadherent  $\rightarrow$  same as #3
- 5. Glibenclamide without problems, no previous problems with metformin, adherent
- a. All doses  $\rightarrow$  metformin 1700 mg +glibenclamide current dose
- 6. Glibenclamide without problems, no previous problems with metformin, nonadherent
  - a. All doses  $\rightarrow$  metformin 1700 mg + glibenclamide 2.5 mg
- 7. Glibenclamide without problems, previous problems with metformin, adherent
  - a. Agrees to take metformin  $\rightarrow$  metformin 850 mg + glibenclamide current dose
    - b. Refuses to take metformin
      - i. Glibenclamide 2.5 mg  $\rightarrow$  glibenclamide 5 mg
      - ii. Glibenclamide 5 mg  $\rightarrow$  glibenclamide 10 mg
      - iii. Glibenclamide 10 mg  $\rightarrow$  glibenclamide 10 mg
- 8. Glibenclamide without problems, previous problems with metformin, nonadherent
  - a. Agrees to take metformin
    - i. Glibenclamide 2.5-5 mg → metformin 850 mg + glibenclamide 2.5 mg
    - ii. Glibenclamide 10 mg  $\rightarrow$  metformin 850 mg + glibenclamide 5 mg
  - b. Refuses to take metform in  $\rightarrow$  continue current glibenclamide dose
- 9. Glibenclamide with hypoglycemia or hypoglycemia symptoms, no previous problems with metformin, adherent
  - a. Glibenclamide 2.5 mg  $\rightarrow$  metformin 1700 mg
  - b. Glibenclamide 5 mg  $\rightarrow$  metformin 1700 mg + glibenclamide 2.5 mg

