  - c. Glibenclamide 10 mg  $\rightarrow$  metformin 1700 mg + glibenclamide 5 mg
- 10. Glibenclamide with hypoglycemia or hypoglycemia symptoms, no previous problems with metformin, nonadherent → same as #9
- 11. Glibenclamide with hypoglycemia or hypoglycemia symptoms, previous problems with metformin, adherent
  - a. Agrees to take metformin
    - i. Glibenclamide 2.5 mg  $\rightarrow$  metformin 850 mg
    - ii. Glibenclamide 5 mg  $\rightarrow$  metformin 850 mg + glibenclamide 2.5 mg
    - iii. Glibenclamide 10 mg  $\rightarrow$  metformin 850 mg + glibenclamide 5 mg
  - b. Refuses to take metformin

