  - h. Metformin 2550 mg + glibenclamide 10 mg → metformin 1700 mg + glibenclamide 5 mg
- 20. Metformin and glibenclamide, problems with metformin, hypoglycemia or hypoglycemia symptoms, nonadherent → same as #19

9≤ A1c ≤14 AND [FBG ≤130(150) OR PPBG ≤180(200)]  $\rightarrow$  Use dosing recommendations for Tx goal< A1c <9

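### Appendix 11: in two cells, a nonadherent patient on glibenclamide 10 mg alone gets 2.5 mg more glibenclamide with hypoglycemia than without it

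*Combined protocol and SAP*

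**What the plan says.** Appendix 11 sets the dose at each A1c visit from A1c, current glucose, regimen, adherence, metformin problems and hypoglycemia. A patient on glibenclamide alone with no previous metformin problem falls in one of four rows:

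- row 5: adherent, no hypoglycemia;
- row 6: nonadherent, no hypoglycemia;
- row 9: adherent, hypoglycemia;
- row 10: nonadherent, hypoglycemia.

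In the table for A1c between goal and 9 with glucose above target, row 6 is headed "6. Glibenclamide without problems, no previous problems with metformin, nonadherent" and moves every dose to metformin 1700 mg with no glibenclamide. Row 10 is "Glibenclamide with hypoglycemia or hypoglycemia symptoms, no previous problems with metformin, nonadherent → same as #9". In the table for A1c 9 to 14 with glucose above target, row 10 again ends "no previous problems with metformin, nonadherent → same as #9", and row 9 there sends a 10 mg patient to "metformin 1700 mg + glibenclamide 5 mg".

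Two cross-references handle glucose at target. For A1c 9 to 14 the instruction is "Use dosing recommendations for Tx goal< A1c <9"; for A1c between goal and 9 it is "Use dosing recommendations for 6≤ A1c ≤Tx goal".

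Section 2.7.2 says medication is stepped down when hypoglycemia symptoms are present, and it plans alpha testing of every scenario before use with patients. Section 3 makes the safety of titration by community health workers a secondary objective.

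**The concern.** Hypoglycemia is the main harm of glibenclamide, and Section 2.7.1 names glibenclamide as the study drug most likely to do harm. With all other inputs equal, a patient who reports hypoglycemia should never leave with more of it than one who does not. In two cells of Appendix 11 the order is reversed.

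The application's output is dispensed at the visit. The medical director reviews it afterwards, within 1 week (Physician Oversight, under Section 7). Incorrect application recommendations are also a primary safety endpoint (Section 4.1.3). If correctness is judged against Appendix 11 as written, these two outputs would count as correct. Alpha testing against the written tables would pass them for the same reason.

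**Working it through.** The check compares written table cells. There is no sample size or power figure to reproduce.

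**Step 1: the two rows.** Glibenclamide output in mg for a nonadherent patient on glibenclamide alone with no previous metformin problem, at current doses of 2.5 / 5 / 10 mg. Difference = row 10 − row 6.

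| Appendix 11 table | Row 6 (no hypoglycemia) | Row 10 (hypoglycemia) | Difference |
|---|---|---|---|
| A1c 5 to <6 | 0 / 0 / 0 | 0 / 0 / 0 | 0 / 0 / 0 |
| A1c 6 to goal | 0 / 0 / 0 | 0 / 0 / 0 | 0 / 0 / 0 |
| Goal to <9, glucose above target | 0 / 0 / 0 | 0 / 0 / 2.5 | 0 / 0 / **+2.5** |
| 9 to 14, glucose above target | 2.5 / 2.5 / 2.5 | 0 / 2.5 / 5 | −2.5 / 0 / **+2.5** |

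Both inversions are at 10 mg: 2.5 − 0 = 2.5 mg and 5 − 2.5 = 2.5 mg. Metformin is 1700 mg in all four outputs concerned, so it does not offset the difference. At 2.5 and 5 mg, row 10 never exceeds row 6.

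**Step 2: the rest of Appendix 11.** Every pair of rows differing only in hypoglycemia was compared across the four tables. Stopping medication and referral to the physician were counted as 0 mg; neither occurs in the two inverted cells.

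| Row pair | Cells | Inverted |
|---|---|---|
| 5 / 9 | 12 | 0 |
| 6 / 10 | 12 | 2 |
| 7 / 11 | 24 | 0 |
| 8 / 12 | 24 | 0 |
| 13 / 17 | 36 | 0 |
| 14 / 18 | 36 | 0 |
| 15 / 19 | 48 | 0 |
| 16 / 20 | 48 | 0 |
| Total | 240 | 2 |

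**Step 3: the at-target cross-reference.** For A1c 9 to 14 with glucose at target, the instruction points to the goal-to-9 recommendations without saying which branch.

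- If it means the goal-to-9 dosing table, the 10 mg patient gets 0 mg without hypoglycemia and 2.5 mg with it, so the inversion carries over.
- If it follows the at-target branch on to the 6-to-goal table, both get 0 mg.

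Of the six A1c and glucose bands from A1c 5 to 14, therefore, 3 are affected on the first reading and 2 on the second.

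**Step 4: comparable rows elsewhere.**

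- Appendix 8, goal to 9: row 3 is "Not taking medications or nonadherent, hypoglycemia or hypoglycemia symptoms → metformin 1700 mg", and row 1 (no hypoglycemia) gives the same. These rows pool patients not taking medication with nonadherent ones.
- Appendix 8, 9 to 14: row 1 (no hypoglycemia) adds 2.5 mg glibenclamide and row 3 (hypoglycemia) adds none. These rows cover only patients not taking medication.
- Appendix 10: rows 5/9 and 6/10 over four glucose bands and three doses give 2 × 4 × 3 = 24 cells, none inverted. In its highest dosing band, row 10 is also a copy ("Glibenclamide with hypoglycemia or hypoglycemia symptoms, no previous problems with metformin, did not take yesterday → same as #9"), but there rows 6 and 10 come out equal. These rows split on whether glibenclamide was taken the day before, not on adherence.

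None of these is an exact match, but none shows more glibenclamide with hypoglycemia.

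**The case against.** The strongest reply is that row 6 is the odd row. In both affected tables, every nonadherent row with hypoglycemia copies its adherent counterpart (10 from 9, 12 from 11, 18 from 17, 20 from 19), so row 10 follows a pattern. Row 6 cuts harder than its neighbors: at 10 mg, row 8 steps down to 5 mg if metformin is accepted, and row 14 continues the dose. If row 6 also stepped 10 mg down to 5 mg, the comparisons would be 2.5 against 5 and 5 against 5, and both inversions would go with row 10 untouched.

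It stands that the two rows could be reconciled from either side and that copying the adherent row is not wrong in itself. Appendix 8 nevertheless supports row 6 in the goal-to-9 band, and raising row 6 would add the riskier drug. The copying pattern is not universal either: in the A1c 5 to <6 table, row 10 stops medication while row 9 gives metformin 1700 mg.

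A second reply also stands: no patient's dose goes up. Row 10 takes 10 mg down to 2.5 mg (75% lower) or 5 mg (50% lower), so Section 2.7.2 is not breached. The fault is relative to the patient without hypoglycemia.

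The third reply is reach. No output of the algorithm newly creates glibenclamide alone without a metformin problem, and every Appendix 11 output for such a patient brings in metformin or stops medication. The state therefore needs a physician override or a patient who quietly drops metformin. The second route is an inference. Appendix 3 asks about each drug separately, and monthly visits repeat the enrollment questions. A metformin problem registers only if the patient volunteers gastrointestinal symptoms and links them to skipping or thinking of stopping. Appendix 10 (fasting glucose 130 to 180, or 150 to 200 with relaxed goals, rows 5 and 6) can then continue glibenclamide alone. The plan does not say whether the prescribed or the reported regimen selects the row. Physician review and telephone advice reduce the risk further, but review comes after dispensing.

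**Conclusion.** The point holds as a low-severity error in the dosing logic. Two of 240 paired cells in Appendix 11 give 2.5 mg more glibenclamide with hypoglycemia than without it, both in the row 6 and row 10 pair at a current dose of 10 mg, with no rationale stated. The count rests on the tables as written and does not depend on how the at-target cross-reference is read; that reading decides only whether a third band inherits the first inversion. The documents do not allow the share of patients affected to be computed, and it is likely to be small. Endpoint analyses and power are unaffected.

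**What to change.** Replace the copy instruction in row 10 with explicit outputs:

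- **Goal to <9, glucose above target:** any glibenclamide dose goes to metformin 1700 mg alone.
- **9 to 14, glucose above target:** glibenclamide 2.5 mg goes to metformin 1700 mg alone; 5 or 10 mg goes to metformin 1700 mg with glibenclamide 2.5 mg.

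Only the two 10 mg outputs change (2.5 to 0 mg, and 5 to 2.5 mg), and the count of inverted cells becomes 0 of 240. State which goal-to-9 branch applies for A1c 9 to 14 with glucose at target.

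Add one check to the alpha testing in Section 2.7.2: with all other inputs equal, the output with hypoglycemia never contains more glibenclamide than the output without it. This tests the tables themselves, which comparing the application with the tables cannot do.

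The cost is two table cells, one clarified cross-reference, a small reprogramming step and one automated check. No new data or patients are needed.
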